**Interventions**

Continence pessary

Participants will be fit for a continence pessary at a fitting appointment by their clinician as per their office protocol. Only continence rings or continence dish pessary will be used. Participants will be instructed on how to remove and reinsert the device so that they can use it at their discretion. Participants will be allowed to use the device during the menses if they desire. They will however be instructed to take the device out during sexual activity. Participants will return to the office at 2 weeks, +/- 4 days for a follow-up visit for assessment and refitting if needed per routine clinical practice. If they feel that the continence pessary needs to be refit, the participants will be asked to call for an earlier follow-up appointment per routine clinical practice.

Poise Impressa®

Participants will be given a sizing kit in the office and asked to select the size that they feel is appropriate per manufacturer's instructions. Once they have selected a size, they will be given a 2-week supply of their size. They will be asked to follow directions on use per the packet insert to simulate "real world use." The packet insert does reflect when the device is not to be used. This includes participants not using this during sexual activity or during their menses. Participants will return to the office at 2 weeks, +/- 4 days for a research visit to assess fit and if needed, change to a different size. At this visit they will be given the remainder of their device supply to complete the study. If they feel that they need a different size, the participants will be asked to contact the research staff for an earlier follow-up visit. Participants may use this device for up to 12 hours in a 24-hour period per the manufacturer's recommendation. As we are assessing efficacy in the setting of typical use, participants will be asked to use this device as they normally would if they were to purchase this on their own for the management of SUI.

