- Participants will also be asked, "If you had a friend or family member with stress urinary leakage, would you recommend this device to them?" Responses included "definitely would recommend," "probably would recommend," neutral or unsure," "probably would not recommend," "definitely would not recommend."
- Participants will also be asked if they have experienced any of the following: vaginal discomfort/pain, vaginal bleeding, vaginal infection, vaginal abrasion or laceration (cut in the vaginal tissues), urinary tract infection (bladder infection), other (with space to write in a response)

Additionally, participants will receive a phone call at 6 months during which general information regarding current device use and satisfaction will be collected via the follow-up questionnaire below. The PGI-I will also be administered verbally during these follow-up calls.

**Follow-Up Questionnaire:** Participants will complete this questionnaire at 6 months with a follow up phone calls and asked to respond to the following questions:

- "Are you still using the device provided to you during the study?"
  - If "yes", they will be asked "How satisfied are you with your current treatment?" Responses include "completely satisfied", "somewhat satisfied", or "not at all satisfied"
  - If "no", they will be asked several questions including:
    - Why are you not using the device? (select all responses that apply): "the device was too difficult to use", "the device did not work", "the device was too expensive", "I am using a different treatment," "I am not bothered by my leakage" or "Other".

- Are you using another treatment? If yes, "what treatment are you using?" with options of pessary, impressa, physical therapy, surgery, other
- They will also be asked the PGI-I

[figure not shown]
**Adverse events (AEs):** Potential AEs of interest include vaginal pain attributed to device use, vaginal bleeding, vaginal infection, vaginal abrasion/laceration, and urinary tract infection. Participants will be instructed to call and report any/all adverse events to research personnel and clinical staff. All AEs will be reported to the IRB of the institution at which the AE occurred (if required by site reporting guidelines), recorded in the research database, and if needed the patient will be scheduled for a clinical assessment. AEs will be assessed at each clinical/research visit and reported with study outcomes.

[figure not shown]

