**Table 1: Study Assessments by Visit**

Evaluation	Baseline	Week 0	Week 2	Week 4
Consent	X			
Demographics	X			
Device Fitting		X	X	
MESA	X			
3-day bladder diary	X			X
UDI-6	X			X
IIQ-7	X			X
FSFI	X			X
Interval Study Questionnaire			X	X
PGI-I				X

At the end of the visit the participant will be given information about the device they were not randomized to use. Participants that were randomized to the continence pessary will be given information on the Poise Impressa® and information on where they can purchase these devices as this would be routine in an office practice. Participants that were randomized to the Poise Impressa® arm can have a pessary fitting scheduled with a provider as part of routine care.

Participants can choose to pursue other options, such as surgery or pelvic floor physical therapy after completion of the study or if they choose to drop out. Participants that desire potential surgery will be scheduled with a physician for further discussion of their options.

This visit is outside of the study and will be considered to be a routine follow up visit.

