#### **Statistical Analysis**

##### **Randomization**

Participants will be randomized to either continence pessary or Poise Impressa® in a 1:1 ratio through random permuted blocks of 4 and 6 stratified by institution. Randomization will be conducted via REDCap to ensure proper randomization and to aid in allocation concealment.

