#### **Sample Size Estimate**

We aim to detect a clinically significant difference of 50% improvement with continence pessary versus 25% with the Poise Impressa®. Assuming an 80% power, an alpha error of 5% and a 20% dropout rate we need 138 participants total (69 per group) to detect this difference. We plan to assess for differences in secondary outcomes between arms while acknowledging that we may be underpowered to detect significant differences in these outcomes.

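### Month-6 satisfaction is asked only of women who say they still use the study device, so comparing it between arms would select on a post-randomisation outcome; month-6 PGI-I shows the effect of assignment, not of the device alone

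*Combined protocol and SAP*

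**What the plan says.** The Follow-Up Questionnaire (III. Methods, Secondary outcomes) opens with "Are you still using the device provided to you during the study". A yes leads to "How satisfied are you with your current treatment", with three response levels. A no leads to reasons for stopping, and no satisfaction item is shown there. Use of another treatment (pessary, Impressa, physical therapy, surgery, other) and the PGI-I are listed outside both branches. The Month 6 Phone Call section confirms that the PGI-I is given in addition to the questionnaire.

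On comparison, the Sample Size Estimate section states: "We plan to assess for differences in secondary outcomes between arms". Specific Aim 2 names satisfaction and likelihood of continued use among the outcomes to be compared.

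On supply, the Background describes Impressa as single use and the pessary as reusable. For Impressa at week 2, the Interventions section says: "At this visit they will be given the remainder of their device supply to complete the study".

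On later treatment, the text after Table 1 says that Impressa-arm women "can have a pessary fitting scheduled with a provider as part of routine care". Pessary-arm women are told where to buy Impressa, and any woman may pursue surgery or physical therapy. The call comes 6 months (within 30 days either way) after week 0, so about five months after the active period.

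**The concern.** Whether a woman still uses her device at month 6 depends on how well it worked and how she liked it. Satisfaction among continuers therefore compares two self-selected groups rather than the randomised arms. A device that most women abandon can look as satisfactory as one that most women keep.

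The screening question adds an imbalance. A pessary user still has the object that the study gave her. An Impressa user at month 6 must be using product that she bought. Taken literally, she may answer no, be recorded as having stopped, and never reach the satisfaction item.

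The month-6 PGI-I asks how leakage is now compared with before the study device. A woman who has since moved to the other device, therapy or surgery reports the result of the whole sequence.

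These are the trial's only data beyond four weeks, and the plan does not say how women who stopped or switched enter either measure.

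**Working it through.** **Plan's own figure.** The inputs are 50% vs 25% success, 80% power, 5% alpha (taken as two-sided) and 20% dropout. With unpooled variance:

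n = (1.960 + 0.842)² × (0.50×0.50 + 0.25×0.75) / 0.25² = 54.9, so 55 per arm; 55/0.80 = 68.75, so 69 per arm and 138 in total.

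This matches the protocol, and nothing below changes it. The 55 per arm is used as the number followed. The documents give no continuation or switching rates, so every such rate below is an assumption.

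**1. Masking among continuers.** Let c be the share continuing and s the share of continuers who are satisfied. The form as printed yields s. The share of all women still using and satisfied is c × s.

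- c = 50% vs 25%, s = 80% in both arms: continuers show 80% vs 80%; all women show 0.50×0.80 = 40% vs 0.25×0.80 = 20%.
- c = 40% vs 20%, same s: continuers again show 80% vs 80%; all women show 32% vs 16%.

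**2. Sensitivity to who continues.** Suppose 50% vs 25% would be satisfied if everyone were asked, 80% of satisfied women continue, and a share b of unsatisfied women continue. With p the true satisfied share, observed satisfaction = 0.8p / [0.8p + b(1 − p)].

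| b, both arms | Pessary | Impressa | Gap (points) | Women asked, of 55 per arm |
|---|---|---|---|---|
| 60% | 57% | 31% | 26 | 38 vs 36 |
| 40% | 67% | 40% | 27 | 33 vs 28 |
| 20% | 80% | 57% | 23 | 28 vs 19 |
| 10% | 89% | 73% | 16 | 25 vs 15 |
| 0% | 100% | 100% | 0 | 22 vs 11 |

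The level is inflated in both arms throughout. The gap holds when many unsatisfied women continue and vanishes when none do. If b differs by arm, say 40% for pessary (already in hand) and 10% for Impressa (must be bought), the result is 0.40/0.60 = 67% vs 0.20/0.275 = 73%, the opposite order to the true 50% vs 25%.

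**3. Screening wording.** If a share m of continuing Impressa users answer no because they bought their own, recorded continuation in that arm is c × (1 − m). In the first example, the share still using and satisfied moves from the true 20% (m = 0) towards 0% (m = 1). This error runs against Impressa, whereas the masking in step 1 runs in its favour.

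**4. Month-6 PGI-I.** Suppose device success is 50% vs 25%, a share w of failures switch, and the new treatment succeeds with probability q. Observed success = p + (1 − p) × w × q. Power is for 55 per arm with a pooled test (78% with no switching).

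| w, q | Pessary | Impressa | Gap (points) | Power |
|---|---|---|---|---|
| 25%, 40% | 55% | 32.5% | 22.5 | 67% |
| 50%, 50% | 62.5% | 43.8% | 18.8 | 50% |
| 75%, 80% | 80% | 70% | 10 | 22% |

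Equal switching only dilutes the gap. Its sign changes only if switching differs sharply by arm: w = 25%, q = 40% for pessary against w = 75%, q = 80% for Impressa gives 55% vs 70%.

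**The case against.** The strongest reply is that no flawed analysis is actually planned. No section specifies a test of satisfaction among continuers. The call is introduced as gathering general information, Table 1 has no month-6 column, and week 4 is headed as the end of study. Satisfaction is also asked of all participants at weeks 2 and 4, so Aim 2 does not depend on the month-6 item. The no branch is introduced as a partial list, so a satisfaction item there cannot be ruled out. An Impressa woman who buys her own and answers no can still name Impressa under other treatment, and expense is among the reasons for stopping, so later purchase was foreseen.

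Much of this stands, and it is why the point is conditional and modest. It does not remove it. The questionnaire sits among outcomes to be compared between arms, nothing declares it descriptive, and the form as printed yields satisfaction only from continuers. The other-treatment answer can recover continued use, but not the satisfaction rating that was skipped.

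Two stronger readings are tempting. The first is that month-6 comparisons say nothing about the randomised devices. The documents do not support that. The proportion still using the device covers every woman reached, and PGI-I is not restricted to continuers, so comparing it by assigned arm is a valid treatment-policy comparison. The second is that the long-term message will be reversed. Reversal appears only under chosen, arm-specific rates that the documents do not give. A PGI-I reversal of that kind would also still be a true statement about assignment.

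**Conclusion.** The concern holds in a limited form. A between-arm comparison of month-6 satisfaction as collected would not be a randomised comparison. Under assumed rates it could turn 40% vs 20% into 80% vs 80%, leave the gap roughly intact, or distort it; which of these applies cannot be known from the documents. The screening wording is unequal by arm and also weakens the proportion still using the device, otherwise the cleanest month-6 measure. How many women would take it literally is unknown. Month-6 PGI-I is sound as an effect of assignment but should not be read as the effect of the device alone. The plan leaves the month-6 estimand undefined. This affects secondary outcomes only: the week-4 primary outcome and N = 138 stand.

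**What to change.** 1. Reword the screening question by arm: *Are you still using a continence pessary / Poise Impressa, including any you bought yourself?* If calls have already been made, use the other-treatment answer to reclassify Impressa-arm women who said no but named Impressa.
2. Compare month-6 satisfaction as still using the assigned device and completely satisfied, with all randomised women as the denominator. State in advance how women not reached are counted, since the Missing Data section gives no rule. Show satisfaction among continuers descriptively only.
3. Label month-6 PGI-I success as treatment-policy, and add a supplementary analysis that counts use of another treatment as non-success.

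If the sponsor does not want formal month-6 comparisons, stating that these results are descriptive would be a simpler alternative.

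The cost is one reworded question and one or two derived analyses, with no added visits. The drawback is that the composite counts a woman who stopped because leakage no longer bothered her as a non-success, so the recorded reasons for stopping should be reported beside it.

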In 2014, the FDA approved an over-the-counter disposable intravaginal device as another nonsurgical treatment for SUI. This device, the Poise Impressa®, is made of a non-absorbable nylon mesh that covers a core with 4 support poles made of resin and is housed in an applicator, similar to that of a tampon applicator(5). It is currently marketed as an over the counter non-surgical treatment of SUI, providing an effective alternative to physical therapy or surgery(6). Ziv et al conducted the initial study on this device, examining it over a 28 day period (comprised of a 14 day trial run followed by a 14 day observation period)(5). The authors found that 85% of participants experienced a  $\geq 70\%$  reduction in pad weight when using the device over the 14 day observation period. They also found that Poise Impressa® use was associated with an improvement in quality of life and had high patient satisfaction (5, 7).

The differences in these two devices are important and may result in major differences in patient satisfaction, compliance, and cost of use. The Poise Impressa® can only be worn up to 12 hours per day and is single use only, whereas the continence pessary can be worn continuously and is both reusable and reimbursable by insurance. To date, there has not been a comparative effectiveness trial performed to address this gap in knowledge. We aim to conduct a randomized comparative effectiveness trial of the continence pessary and the Poise Impressa® in order to provide patients and providers knowledge of the best nonsurgical treatment for women with SUI. We hypothesize that a physician fit continence pessary will provide greater subjective improvement in SUI symptoms, greater improvement in quality of life, greater patient satisfaction, and be lower cost as compared to the Poise Impressa®.

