## II. SPECIFIC AIMS

**Specific Aim 1: To compare SUI symptom improvement between a continence pessary and the Poise Impressa® device.** Improvement will be assessed using the Patient Global Impression of Improvement (PGI-I), a validated questionnaire assessing symptom changes(8).

**Specific Aim 2: To compare quality of life, patient satisfaction, ease of device use, likelihood of continued use, and rates of adverse events between the continence pessary versus the Poise Impressa®.** We will use validated questionnaires to assess participants' quality of life (9, 10). We will monitor for adverse events that are related or possibly related to the study device such as pain, vaginal bleeding, infections, and lacerations. We will use a Likert scale to assess patient satisfaction, ease of device use, comfort, and likelihood of continued use.

**Specific Aim 3: To evaluate cost of use associated with each device.** We will use cost of clinic visits and the cost of the device(s) to calculate estimated costs associated with device utilization.

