**Secondary outcomes:**

**Quality of life (QoL):** Participants' QoL will be assessed with the following three validated questionnaires:

1. Urogenital Distress Inventory (UDI-6)(9, 12): This short form 6-item questionnaire measures urinary incontinence symptom bother.
2. Urinary Incontinence Impact Questionnaire (IIQ-7)(9, 12): This short form 7-item questionnaire measures the functional impact of urinary incontinence.
3. Female Sexual Function Index (FSFI)(13): This 19-item questionnaire is used to assess sexual functioning in women.

These questionnaires will be completed by participants at baseline and then again at the end of the 4-week study period. A change score will be calculated by subtracting the two scores.

**Interval Study Questionnaire:** Participants will complete this questionnaire at weeks 2 and 4. It consists of questions addressing menstrual status, device use, adverse events, and Likert scale questions assessing *device satisfaction, ease of use, comfort, and likelihood of continued use*. The questions will consist of the following:

- "Did you have your period during the last 2 weeks?"
  - If yes, "During the last two weeks, how many days were you on your period?" and "During the last two weeks, how many days did you wear your device?"
- "On average, how many hours a day did you wear your device?"
- "How satisfied were you with the device?" Participants may respond with "completely satisfied," "somewhat satisfied," or "not at all satisfied," "(14)." Responses include "completely comfortable," "somewhat comfortable," "not at all comfortable."
- "In general, how comfortable is the device?" Responses include "completely comfortable," "somewhat comfortable," "not at all comfortable."
- Ease of use will be assessed by asking "how easy/difficult was the device to use?", "how easy/difficulty was the device to insert?" and "how easy/difficult was the device to remove?" Responses will include "very easy," "easy," "somewhat easy," "somewhat difficult," "difficult," "very difficult."
- Likelihood of continued use will be assessed using the same Likert scale ranging from "strongly disagree" to "strongly agree" and asking participants to rate their level of agreement with the statement "I would continue to use this device in the future."

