**Cost analysis:** For the Poise Impressa® device, cost calculations will include cost of sizing kit and devices, as well as costs associated with any refits. For the continence pessary, cost calculations will include the cost of the device, initial fitting visit and any additional clinic visits. Cost will be extrapolated to estimate annual cost of use for each device.

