#### *Week 2 Visit*

All participants will complete the Interval Study Questionnaire and report on adverse events. All patients randomized to the continence pessary will undergo a pelvic exam per routine clinical practice to be assessed for possible refitting. Occurrence of any adverse events will also be assessed at that time. Participants randomized to the Poise Impressa® device will meet with research staff to assess size and if needed undergo resizing and will receive an additional 2-week supply of appropriately sized devices. For those participants in the Poise Impressa®, only those reporting symptoms concerning for adverse events will undergo pelvic exam by a clinical provider, otherwise an exam will be deferred in this group.

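### No count of single-use Impressa devices consumed is described, so Aim 3's annual cost of use would rest on a proxy that the plan does not name

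*Combined protocol and SAP*

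**What the plan says.** Specific Aim 3 is a comparison of cost: "We will use cost of clinic visits and the cost of the device(s) to calculate estimated costs associated with device utilization". The Background hypothesises that the pessary will be the cheaper option. The Cost analysis paragraph lists the Impressa components ("cost calculations will include cost of sizing kit and devices, as well as costs associated with any refits") and adds: "Cost will be extrapolated to estimate annual cost of use for each device". It gives no unit price and does not say whether the devices to be costed are those used or those dispensed.

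The Background describes the product: "The Poise Impressa® can only be worn up to 12 hours per day and is single use only". The Interventions section repeats the limit as "Participants may use this device for up to 12 hours in a 24-hour period", which restricts hours and not the number of devices. It also leaves the amount of use to the woman and excludes use during sexual activity and menses.

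The use data described are:

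- **Interval Study Questionnaire (weeks 2 and 4):** days worn in the last two weeks, and "On average, how many hours a day did you wear your device".
- **Six-month Follow-Up Questionnaire:** whether the device is still in use, yes or no.
- **Supply:** two weeks' worth at week 0, and at week 2 participants "will receive an additional 2-week supply of appropriately sized devices". The number of devices in a supply is not given.

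Neither the questionnaire items, the visit descriptions nor Table 1 mention a count of devices used, or a return or count of unopened ones.

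**The concern.** The sizing kit and refits are occasional costs. The devices recur, so the device part of an annual cost is unit price times devices consumed per unit of time. That rate is not among the data described, and neither available proxy supplies it.

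Hours and days do not convert to devices. A woman who removes a single-use device and wants support again the same day needs another one, so ten hours of wear may be one device or two.

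Supply does not equal use either. Use is discretionary and stops during menses, and resizing can leave devices of the wrong size unopened. The week-2 visit has a window of 4 days either way, so the first supply covers anything from 10 to 18 days. Devices are free in the trial (Participant Cost), so participants' own purchases would not record use of the study supply.

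At stake is the size of the cost difference that Aim 3 would report. The two proxies err in opposite directions, and because the costing basis is not named it could be chosen after the results are known. Consumption that was not recorded cannot be reliably reconstructed at analysis.

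**Working it through.** The plan states no device count, unit price or cost total, so there is no figure of its own to reproduce. The check is whether the described data determine the device count.

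**Inputs.** D = days worn in 14 (asked in the Interval Study Questionnaire). k = devices per day worn (not asked; at least 1 because each device is single use). S = devices in a two-week supply (not stated; 14, one a day, is assumed below).

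**Identity.** Devices in two weeks = D × k; annual devices = D × k × 365/14. D is asked and k is not. Average hours do not give k.

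**Bounds.** Consumption of study devices lies between D (k = 1) and S. For a woman reporting 10 of 14 days with S = 14:

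- floor: 10 × 365/14 = 261 devices a year
- ceiling: 14 × 365/14 = 365 devices a year

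At 7 of 14 days the floor is 7 × 365/14 = 182.5 and the ceiling is again 365. With k = 2 on 10 days she would need 20 devices (521 a year), which is possible only if S exceeds 14. Identical, complete answers are therefore compatible with a range of counts, but not an unlimited one.

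**Error from costing by days worn.** If a share f of wear-days uses a second device, true use is D(1 + f), and the understatement is 1 − 1/(1 + f):

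| f (assumed) | Calculation | Understatement |
|---|---|---|
| 10% | 1 − 1/1.1 | 9% |
| 20% | 1 − 1/1.2 | 17% |
| 30% | 1 − 1/1.3 | 23% |

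With S = 14 these need D(1 + f) ≤ 14, that is D of at most 12, 11 and 10 whole days respectively.

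**Error from costing by supply.** If the supply is one device a day and one device is worn on d days a week, the overstatement is 7/d − 1:

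| d (assumed) | Calculation | Overstatement |
|---|---|---|
| 6 | 7/6 − 1 | 17% |
| 5 | 7/5 − 1 | 40% |
| 4 | 7/4 − 1 | 75% |
| 3 | 7/3 − 1 | 133% |

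The second table assumes one device per wear-day, under which days worn would be exactly right. It measures the consequence of choosing the supply as the basis, not of the missing count, so the tables must not be combined. All percentages apply to the device component, not to total Impressa cost.

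**The case against.** Aim 3 promises only estimated costs, and a model built on days worn or on supply meets that wording. A reader might infer that Aim 3 cannot be carried out; the documents do not support that. What is lost is a cost based on observed consumption.

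A reader might also infer that no count will exist. The case report forms mentioned under Data Storage and the bladder diary fields are not shown, and staff who hand out devices may keep a dispensing log. The supportable statement is that no count is described. A log of devices dispensed alone would still record supply and not use.

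The 133% figure is tempting as a headline, but it belongs to the choice of the worse proxy, and nothing in the plan says supply will be used. The understatement of 9% to 23% rests on an assumed frequency of second devices; no section reports or expects more than one a day. Nor can one say that Impressa cost is nearly all device cost, since no kit, device or visit price is given.

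Counting days is also conservative for the stated hypothesis, because it lowers the Impressa cost. Only counting supply favours it.

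Finally, the days item is laid out under a yes to the question about periods, so some women may never be asked it. That is a separate gap and arguably a larger one, since it can remove the floor. Closing it would still not reveal devices per wear-day. These objections limit the wording and the weight of the point; they do not supply the missing quantity.

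**Conclusion.** The point holds in limited form. The plan projects an annual cost of use for a single-use product without describing any record of units consumed, and without naming the quantity to be costed. Where the days item is answered, use of study devices is bounded below by days worn and above by devices dispensed, but is not observed.

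Under the assumed second-device rates, costing by days understates the device component by 9% to 23%. Under an assumed one-a-day supply with 6 down to 3 wear-days a week, costing by supply overstates it by 17% to 133%. Both ranges are illustrations, because the documents give neither the supply size nor the pattern of use. Whether the direction of the cost comparison would change cannot be judged without prices. This is a cheap improvement to a secondary aim; the PGI-I outcome and the sample size of 138 are untouched.

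**What to change.** At the existing week-2 and week-4 visits, record for every Impressa participant the devices dispensed since the last visit (including any early resizing) and the unopened devices remaining, by size. Devices used in an interval are then those on hand at its start, plus any dispensed during it, minus those unopened at its end. If none are brought back, ask how many devices she has used since her last visit.

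In the Cost analysis paragraph, state three things:

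- Annual device cost is based on devices used per day of follow-up.
- Wrong-size devices left over after resizing are costed under refits, so that they are not given a cost of zero.
- Costing by days worn and by supply dispensed is shown as lower and upper sensitivity bounds. The lower bound is available only for women who are asked the days item.

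The cost is one added form field and a reminder to bring back unopened devices. Some women will forget, and the recall question carries error. A four-week count of free devices may also differ from a year of purchased use, which the report should say. No new visit or procedure is needed.
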